## 6.7 Radiostereometric Analysis (RSA)

The RSA analysis will be the responsibility of the Canadian RSA Network. In summary, model based RSA software (RSAcore, Leiden, Netherlands) will be used for analysis, employing computer-models of the DePuy Synthes implants and inserted beads representing the bone rigid body. A central analysis service will be employed to analyze anonymized radiographs in a standard manner. DePuy Synthes will provide production CAD models as required for this analysis.

Three-dimensional migration measurements will be made of the acetabular shell relative to the bone beads. The 6-week examination will be used as reference against which the 3-month, 6-month, 1-year and 2-year post-operative exams will be compared. Results obtained from the model based RSA software will be changes from the 6-week (baseline) examination and will report the following at 3 months, 6 months, 1 year and 2 years:

- X, Y and Z translation measurements in mm from baseline;
- X, Y and Z rotation measurements in degrees from baseline;
- Maximal total point motion (one measurement in mm of maximal migration).

Three-dimensional migration of the Pinnacle Acetabular Shell shall be determined from the software.

Linear head penetration (in mm) will be performed by examining the change in distance between the center of the femoral head and the center of the acetabular shell between the 6-week (baseline) exam and 1 year and 2 year exam. The femoral head center is determined by fitting a CAD sphere to the articular region of the femoral head (ignoring the trunnion area). The acetabular shell center is determined in a similar manner but also uses the silhouette of the cup face to determine its' centerpoint.

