#### 1.1.2 Secondary Objectives

The secondary objectives are:

- To establish the subsidence profile of the Pinnacle Acetabular Shell; this will be accomplished by determining the mean subsidence at 3 months, 6 months and 1 year as measured with RSA.
- Other RSA measurements (X and Z translations in mm, X, Y, and Z rotations in degrees, and maximal total point motion in mm) at all time points.
- Functional and health status will be measured with Harris Hip Score, HOOS Jr. and Forgotten Joint Score (FJS-12).
- Analysis of cup positioning (inclination and version)
- Linear head penetration: Linear head penetration (in mm) will be performed by examining the change in distance between the center of the femoral head and the center of the acetabular shell between the 6-week (baseline) exam and the 3 months, 6 months, 1 year and 2 year exam. The femoral head center is determined

by fitting a CAD sphere to the articular region of the femoral head (ignoring the trunnion area). The acetabular shell center is determined in a similar manner but also uses the silhouette of the cup face to determine its' centerpoint.

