### **3 Levels of Significance**

There are no specific hypotheses being tested in this study. To facilitate clinical interpretation, confidence intervals will accompany primary and secondary endpoint estimates and will be 2-sided 95% confidence intervals; these confidence intervals are considered to be exploratory.

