## 6 Analyses to be Conducted

### 6.1 General Conventions

All statistical analyses will be performed using SAS® Version 9.4 or higher, unless otherwise noted. Standard descriptive summaries for continuous data include the number of subjects with non-missing observations (n), mean, standard deviation (SD), median, minimum, and maximum values. For categorical data, the count and percentage will be provided. Percentages will be based on the number of subjects without missing data. If exploratory tests of hypotheses are performed, t-tests will be performed for continuous variables, and Fishers' Exact Test will be performed for categorical variables. Baseline for the RSA analysis is 6 weeks with the exception of the exploratory analysis of the subset where RSA data is available prior to discharge. Baseline for the Forgotten Joint Score and for linear head penetration is also 6 weeks. Baseline for all other endpoints is the pre-operative measurements collected before surgery. Unless specifically stated otherwise, all endpoints will be analyzed by surgical approach and overall, pooling all surgical approaches.

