## **6.7 Secondary Endpoints**

### 6.7.1 RSA Measured Subsidence and maximal total point motion at 3 months, 6 months, 1 year, and 2 years

X, Y, and Z translations from week 6 in mm and A, Y, and Z rotations in degrees, and maximal total point motion in mm will be summarized at the 3 month, 6 month, 1 year, and 2 years visit windows using the Per Protocol Analysis Set and the Safety Set. Standard continuous summaries will be provided along with 95% confidence intervals. These summaries will be provided for each surgical approach, as well as combined.

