### 6.7.3 Linear head penetration at 6 weeks, 3 months, 6 months, 1 year, and 2 years

Linear head penetration (in mm) is the change in distance between the center of the femoral head and the center of the acetabular shell between the 6-week (baseline) exam and the 3 months, 6 months, 1 year and 2 year exam. The distance between the centers within each visit window will be summarized and the change from baseline will be provided using the Per Protocol Analysis Set.

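### Linear head penetration is the change in an unsigned centre-to-centre distance, so it can understate head movement or reverse its sign; signed components and a caveat should be added (minor)

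*SAP*

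**What the plan says.** Protocol 6.7 bases linear head penetration on "the change in distance between the center of the femoral head and the center of the acetabular shell", from the 6-week exam to 1 and 2 years. SAP 1.1.2 repeats the definition ("Linear head penetration (in mm) will be performed by examining the change in distance") and extends it to 3 and 6 months. SAP 6.7.3 sets the output: "The distance between the centers within each visit window will be summarized and the change from baseline will be provided".

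Both centres are fitted at each exam. Protocol 6.7 says "The femoral head center is determined by fitting a CAD sphere to the articular region of the femoral head"; the shell centre is found in a similar way, with the cup-face silhouette as well. Neither document lists a direction or components for the head relative to the shell.

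Shell migration is handled by axis. Protocol 6.7 lists "X, Y and Z translation measurements in mm from baseline" and SAP 6.7.1 summarises "X, Y, and Z translations from week 6 in mm".

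Four other provisions bear on the point:
- Continuous summaries include "mean, standard deviation (SD), median, minimum, and maximum values" (SAP 6.1), and "confidence intervals will accompany primary and secondary endpoint estimates" (SAP 3).
- Protocol 3.2 names head penetration as a secondary endpoint, by approach and combined.
- Protocol 3.5 leaves the liner type to the surgeon, including +4 and 10-degree options.
- Protocol 6.4 plans a duplicate RSA exam at 6 weeks to estimate measurement error; no error value is given.

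**The concern.** A distance has no direction. If the two centres are already apart at 6 weeks, a head that moves sideways to that offset barely changes the distance, and a head that moves back towards the shell centre shortens it. Both are real movement, yet the rule returns about zero in one case and a negative number in the other.

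The documents do not say that the centres coincide at 6 weeks, and with several liner types allowed a common concentric geometry cannot be presumed. At stake is how a named secondary endpoint is read. From a small or negative mean, the reader could not separate little movement from movement across or against the baseline offset.

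**Working it through.** The plan states no figure for this endpoint, so there is none to reproduce. All numerical inputs below are assumptions.

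**Notation.** b is the vector from shell centre to head centre at 6 weeks, with length d0. m is the head's true displacement relative to the shell, with length p. a is the angle between b and m. The planned endpoint is |b + m| - |b|.

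**Bound.** By the triangle inequality, |b + m| - |b| <= |m|. Equality holds only if b = 0, if m points the same way as b, or if m = 0.

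**No measurement error.** Change = sqrt((d0 + p cos a)^2 + (p sin a)^2) - d0, with p = 0.10 mm. For example, d0 = 0.1 and a = 90 degrees gives sqrt(0.01 + 0.01) - 0.1 = 0.041; d0 = 0.5 and a = 90 degrees gives sqrt(0.25 + 0.01) - 0.5 = 0.010.

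| Offset d0 (mm) | 0 deg | 45 deg | 90 deg | 135 deg | 180 deg |
|---|---|---|---|---|---|
| 0 | 0.100 | 0.100 | 0.100 | 0.100 | 0.100 |
| 0.1 | 0.100 | 0.085 | 0.041 | -0.023 | -0.100 |
| 0.5 | 0.100 | 0.075 | 0.010 | -0.065 | -0.100 |
| 4 | 0.100 | 0.071 | 0.001 | -0.070 | -0.100 |

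**With measurement error.** Take errors e0 and e1 on the centre-to-centre vector with the same distribution at both exams. Then E|b + m + e1| - E|b + e0| = E(|b + m + e| - |b + e|) <= |m|. The upper bound therefore holds for the mean. It does not hold for each reading: a single measured change can exceed the displacement.

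For independent normal error with SD s per axis, a true distance D has expected measured value s[sqrt(2/pi) exp(-k^2/2) + (k + 1/k) erf(k/sqrt 2)], where k = D/s; at D = 0 it is 2s sqrt(2/pi).

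- Concentric centres, s = 0.05, p = 0.10: at follow-up k = 2, giving 0.05 x (0.798 x 0.135 + 2.5 x 0.9545) = 0.1247. At 6 weeks it is 0.0798. The mean change is 0.045 mm.
- The same with s = 0.02 gives 0.072 mm, and with s = 0.10 gives 0.025 mm.
- Movement along the offset, s = 0.05: 0.088 mm at d0 = 0.1, 0.099 mm at d0 = 0.5 and 0.100 mm at d0 = 4. The bias from error fades as the offset grows.
- d0 = 0.1 and s = 0.05 at the five angles: 0.088, 0.074, 0.034, -0.017 and -0.045 mm.

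**Alternatives at s = 0.05 and p = 0.10.** Signed components have no bias in the mean. At 45, 90 and 135 degrees, the components along and across the offset average 0.071 and 0.071, 0.000 and 0.100, and -0.071 and 0.071 mm. The 3D length of the displacement is biased upward: it averages 0.147 mm, and 0.113 mm when nothing has moved.

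**The case against.** The strongest reply is that the plan contains no error in its own terms. The definition is the same in all three places, and neither document says that penetration is meant to equal the length of the head's displacement vector. The illustrative offsets and angles are chosen, and nothing in the documents makes movement at 90 to 180 degrees to the offset likely. The distance is also summarised at each visit with minimum and maximum, so a non-zero 6-week offset and any negative change will be seen. Components have faults of their own: more noise, and means that shrink when subjects move in different directions.

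Most of this stands. It makes the point a limit of the measure rather than a contradiction, and it keeps the severity low. It does not remove the point: the planned summaries show no direction, and SAP 6.13 plans no sensitivity analyses, so no other measure of head movement would be reported.

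A reader might also go too far the other way, in three respects:
- That the scalar is valid only if error is negligible at both exams. For a group mean this is too strong. With movement along a 0.5 mm offset and error SD 0.05 mm, the mean is 0.099 mm for a true 0.10 mm.
- That every subject's value is too low. The bound holds without error or on average, not for each reading.
- That the +4 liners imply a 4 mm offset between the centres. The documents do not say so; 4 mm is used above only as the end of an assumed range.

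**Conclusion.** The point holds as a minor one. As defined, linear head penetration can understate the head's movement relative to the shell or reverse its sign. It recovers that movement without loss only when the 6-week centres coincide, when movement follows the baseline offset, or when nothing moves, and in each case without error. Error adds material downward bias to the mean only where the offset is small relative to the error: 0.045 mm for a true 0.10 mm with concentric centres and an assumed SD of 0.05 mm per axis.

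The size in this study is unknown, because the documents give no offset, direction of movement or error. A reader might infer that the reported penetration will be wrong here; the documents support only that it can be. The endpoint is descriptive, with no hypotheses and with exploratory confidence intervals. The primary endpoint and the sample size are unaffected.

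**What to change.** Keep the scalar as defined, and state beside it that it can understate head movement or reverse its sign. In Protocol 6.7 and SAP 1.1.2 and 6.7.3:
- Add the signed X, Y and Z components of head-centre displacement relative to the shell centre, from 6 weeks to each follow-up.
- Use the coordinate frame and sign convention already used for the shell translations, with left and right hips mirrored to one side.
- Correct for any shell rotation between exams, or state that it is not corrected.
- Summarise each component with mean and 95% CI, by approach and combined. All three are needed, since no single axis need show the whole movement.
- Give any 3D magnitude only as supplementary, because error biases it upward.
- Report the 6-week duplicate-exam error for these centres where it is available.

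**Cost.** No new data collection. The additions are three variables at up to four visits and four groupings (three approaches and combined): 3 x 4 x 4 = 48 summaries. The central RSA service must supply centre coordinates that it already fits but that Protocol 6.7 does not list among the software results.

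Components are noisier when the offset is small. At an assumed SD of 0.05 mm per axis and concentric centres, the per-subject error SD is 0.05 x sqrt 2 = 0.071 mm, against a simulated 0.056 mm (0.0555 unrounded) for the scalar. At n = 30, 2SE from error alone is 2 x 0.0707/sqrt 30 = 0.026 mm against 2 x 0.0555/sqrt 30 = 0.020 mm.

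Mean components also shrink when directions differ between subjects. For 0.10 mm spread evenly over +/-45 or +/-90 degrees in a plane, the mean along the central axis is 0.1 x sin(45 deg)/(pi/4) = 0.090 mm or 0.1 x 2/pi = 0.064 mm. That is a reason to keep the scalar beside the components.

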### 6.7.4 Harris Hip Score at Pre-Op, 6 weeks, 3 months, 6 months, 1 year, and 2 years

Harris hip scores are assessed at the Pre-Op visit and at 6 weeks, 3 months, 6 months, 1 year and 2 years. Results within each visit window will be summarized and changes from baseline will be provided using the Per Protocol Analysis Set. Standard continuous summaries will be supplemented with 95% confidence intervals.

### 6.7.5 HOOS Jr. Score at Pre-Op, 6 weeks, 3 months, 6 months, 1 year and 2 years

HOOS Jr. scores are assessed at the Pre-Op visit and at 6 weeks, 3 months, 6 months, 1 year and 2 years. Results within each visit window will be summarized and changes from baseline will be provided using the Per Protocol Analysis Set. Standard continuous summaries will be supplemented with 95% confidence intervals.

### 6.7.6 Forgotten Joint Score (FJS-12) at 6 weeks, 3 months, 6 months, 1 year and 2 years

FJS-12 scores are assessed at 6 weeks, 3 months, 6 months, 1 year and 2 years. Results within each visit window will be summarized and changes from baseline will be provided

using the Per Protocol Analysis Set. Standard continuous summaries will be supplemented with 95% confidence intervals.

#### 6.7.7 Hip Evaluation at Pre-Op, 6 weeks, 3 months, 6 months, 1 year and 2 years

Hip evaluation questions will be summarized at Pre-Op, 6 weeks, 3 months, 6 months, 1 year and 2 years as categorical data using the Per Protocol Analysis Set. The first two questions (“How satisfied are you with this procedure?” and “Would you have this procedure again?”) will not be summarized at the Pre-Op visit.

### 6.8 Exploratory Endpoint Analysis

Exploratory analyses will include the following:

- Summaries of RSA measured subsidence at 6 Weeks, 3 months, 6 months and 1 year and 2 years will be conducted on the subset of subjects where RSA data was obtained prior to discharge;
- Correlation of cup position at 6 weeks and cup migration across surgical approaches (pooled) as well as by surgical approach;
- Correlation of functional and health status outcomes (Harris Hip Score, HOOS Jr., and FJS-12) vs. RSA observations may be explored.

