### 6.2 Operative (Day 0)

Each subject will receive an uncemented Corail femoral stem in combination with a Pinnacle Sector Acetabular cup. All subjects will receive a metal femoral head and an AltrX Polyethylene liner. No screw fixation of the Sector cup is allowed by this protocol. If the surgeon deems that screw fixation or any component other than those listed in the protocol is required for that subject, that subject will be withdrawn from the study. Subjects that are withdrawn pre-operatively or intra-operatively will be replaced in order to have 30 subjects in each surgical approach.

Three surgical approaches will be used for the purpose of this study: posterior, anterior, and lateral. Each surgeon shall perform the approach they are most comfortable with and have the greatest expertise. In general, subjects enrolled at the Winnipeg site will undergo a posterior approach or direct lateral approach. Subjects enrolled at the London site will undergo a direct anterior approach, direct lateral approach or posterior approach. Enrollment will be closely monitored to ensure a minimum of 30 subjects are enrolled in each surgical approach group. Once a group has reached 30 implantations, Investigators of that approach group will be informed to halt enrollment of further subjects. If over 30 subjects are enrolled per approach, the additional subjects will be treated as any other study subject (i.e. exams, follow-up, analysis).

Implant sizing shall be performed as per the surgeon's discretion for each individual subject and will not be standardized between sites. Approximately 5-10 tantalum beads will be placed into the

acetabulum. Bead placement will be standardized across study sites to reduce the possibility of unuseable RSA exams resulting from poor bead spacing or bead occlusion.

Any intra-operative adverse events will be captured as well as details of the surgery and implants/components used. The information collected from the 'Operative' time-point will be populated on the appropriate eCRFs as indicated in the Time and Events Table (Section 1.1).

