### 9.2 Treatment Assignment

Subjects enrolled will undergo THA using the study devices listed in Section 3.5 and one of the surgical approaches under study: posterior, anterior, and lateral. Centers will be selected for their expertise in one or more of the surgical approaches. Each surgeon will perform the approach they are most comfortable with and have the greatest expertise. In general, subjects enrolled at the Winnipeg site will undergo a posterior approach or direct lateral approach. Subjects enrolled at the London site will undergo a direct anterior approach, direct lateral approach or posterior approach. Enrollment will be closely monitored to ensure a minimum of 30 subjects are enrolled in each surgical approach group. Once a group has reached 30 implantations, Investigators of that approach group will be informed to halt enrollment of further subjects.

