## **9.8 Sample Size Justification**

This study sample size was established to provide adequate precision on the mean subsidence estimate at 2 years for each surgical approach. A common standard deviation of 0.2 mm is anticipated. Based upon this standard deviation and a sample size of N=30, a 2-sided 95% confidence interval for each respective surgical approach is anticipated to have a margin of error equal to approximately  $2SE = 2 \times \frac{SD}{\sqrt{n}} = 2 \times \frac{0.2}{\sqrt{30}} = 0.073$  mm. This margin of error was deemed to be an adequate level of precision by the Sponsor.

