### **5 Sample Size Justification**

This study sample size was established to provide adequate precision on the mean subsidence estimate at 2 years for each surgical approach. A common standard deviation of 0.2 mm is anticipated. Based upon this standard deviation and a sample size of N=30, a

2-sided 95% confidence interval for each respective surgical approach is anticipated to have a margin of error equal to approximately  $2SE = 2 * \frac{SD}{\sqrt{N}} = 2 * \frac{0.2}{\sqrt{30}} = 0.073mm$ . This margin of error was deemed to be an adequate level of precision by the Sponsor.

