### 6.7.2 Cup Positioning at 6 weeks

Inclination and version will be assessed at 6 weeks from the AP radiographs using Martell software. Summaries will be provided using the Per Protocol Analysis Set.

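### The pooled correlation of cup position with migration (SAP 6.8) is not adjusted for surgical approach, and no combined within-approach estimate is planned beside it.

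*SAP*

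**What the plan says.** SAP 6.8 (Exploratory Endpoint Analysis) plans "Correlation of cup position at 6 weeks and cup migration across surgical approaches (pooled) as well as by surgical approach". Under SAP 6.7.2, cup position means two angles: "Inclination and version will be assessed at 6 weeks from the AP radiographs using Martell software". SAP 6.8 does not name the type of coefficient, the migration component or time point, or any adjustment for the pooled figure.

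Reporting both ways follows the general rule in SAP 6.1: "Unless specifically stated otherwise, all endpoints will be analyzed by surgical approach and overall, pooling all surgical approaches".

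Approach is not randomized. Protocol 6.2 says "Each surgeon shall perform the approach they are most comfortable with and have the greatest expertise", and Protocol 9.2 repeats this. Approach is also partly tied to site. Protocol 9.2 says "Subjects enrolled at the London site will undergo a direct anterior approach, direct lateral approach or posterior approach", whereas for Winnipeg it names only the posterior and direct lateral approaches.

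No other section supplies an approach-adjusted combined correlation. SAP 6.13 plans no sensitivity analyses and SAP 6.15 no formal look at site homogeneity. SAP 3 states that no hypotheses are tested and that the confidence intervals are exploratory.

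**The concern.** The question behind the bullet is whether, among cups implanted in the same way, inclination or version goes with more migration. A raw coefficient over all cups answers a different question. It adds the covariance of the three approach means to the relation inside the approaches. Because approach goes with surgeon and partly with site, differences between the approach means may reflect surgeon, site or case mix as well as technique.

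The pooled coefficient could therefore suggest that cup angle goes with migration when it does not within any approach, or could hide a relation that is present within all of them. The three separate coefficients do not have this problem, but with about 30 cups each they are wide. The only precise estimate in the plan is the one open to the distortion.

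**Working it through.** **The plan's own figure.** The documents state no figure for this correlation. Their one design figure concerns the mean: 2 × 0.2/√30 = 0.073 mm (Protocol 9.8, SAP 5), which reproduces. It matters here only for its inputs: "A common standard deviation of 0.2 mm is anticipated", and 30 subjects per approach (90 in all).

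**Assumptions, not in the documents.** Three equal groups with equally spaced means. dx and dy are the steps between adjacent approaches in cup position and in migration, in within-approach SDs. The within-approach correlation r_w is the same in each approach. Group means on one line give the largest between-approach covariance for a given spread, so other patterns would do less. To express dy in mm, migration is taken as 2-year Y translation with SD 0.2 mm.

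**Formula.** The group means (-d, 0, d) have variance (2/3)d², so

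r_pooled = [r_w + (2/3)·dx·dy] / √[(1 + (2/3)dx²)(1 + (2/3)dy²)]

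**A correlation created (r_w = 0).** Rejection rates are for a nominal two-sided 5% test in 20,000 simulated studies of 3 × 30. The SAP specifies no such test, so they serve only as a scale.

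| dx | dy | dy in mm | Calculation | Pooled r | Test rejects |
|---|---|---|---|---|---|
| 0.25 | 0.25 | 0.05 | 0.0417/1.0417 | 0.04 | 7% |
| 0.5 | 0.5 | 0.1 | 0.1667/1.1667 | 0.14 | 27% |
| 1 | 0.5 | 0.1 | 0.3333/√(1.6667 × 1.1667) | 0.24 | 65% |
| 1 | 1 | 0.2 | 0.6667/1.6667 | 0.40 | 99% |

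The extreme approaches differ by twice the step. If dx = 0 or dy = 0, the numerator is 0 and no correlation is created.

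**A correlation hidden (r_w = -0.30).**
- At 0.5/0.5: (-0.30 + 0.1667)/1.1667 = -0.11. Detection is about 17% of runs, against about 82% for the within-approach analysis.
- At 0.67/0.67: (-0.30 + 0.2993)/1.2993 = 0.00. Detection is about 4%.
- If approaches differ on one variable only, a true correlation of 0.30 is merely weakened: 0.30/√1.1667 = 0.28 at a 0.5 SD step, and 0.30/√1.6667 = 0.23 at 1 SD.

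**Precision of the by-approach coefficients** (Fisher z, full n = 30, no losses). At r = 0: tanh(±1.96/√27) = -0.36 to 0.36. At r = 0.30: -0.07 to 0.60.

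**The adjusted alternative.** Centre both variables on their approach means and correlate the residuals (86 df). In simulation with r_w = 0, the mean is 0.00 and the 5% test rejects 5.0% to 5.2% of runs in every scenario. With r_w = ±0.30, the mean is about ±0.30. The 95% half-width at r = 0 is tanh(1.96/√85) = 0.209, against tanh(1.96/√87) = 0.207 unadjusted.

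**The case against.** The strongest reply is that the same bullet already plans the correlation by approach. Those coefficients are free of the artefact and will sit beside the pooled one. That stands: a reader who infers that the analysis as a whole ignores approach is going beyond the text. It does not fully close the gap, because a pooled 0.24 next to three intervals of about ±0.36 would not show which explanation holds.

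Second, the artefact needs approaches to differ on both variables. The documents neither state nor exclude this, and at steps of 0.25 SD it is negligible. That also stands, and it is why the size is given as a range.

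Third, a marginal correlation over all implanted cups is a legitimate description in a non-controlled study without hypotheses. This is a good reason to keep the raw figure and label it rather than remove it.

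Two further inferences are tempting and unsupported. One is that the pooled figure will be the one quoted; nothing in either document says so. The other is that it would mislead product development. Protocol 9.14 and SAP 6.10 give that purpose to the 1-year interim summary of subsidence, not to this correlation.

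**Conclusion.** The point holds as a minor gap in an exploratory analysis. The pooled coefficient is unadjusted for a non-randomized factor, and no combined within-approach estimate is specified.

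Under the assumed steps, the distortion when there is no within-approach correlation runs from none (approaches differ on one variable only) through 0.04 to 0.40. A true -0.30 could shrink to -0.11 or vanish. All of this rests on assumed between-approach differences, so the documents support saying that the pooled coefficient can mislead, not that it will. The primary endpoint, its confidence intervals and the sample size are untouched.

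**What to change.** In SAP 6.8:
- Add a combined within-approach (partial) correlation of inclination, and separately of version, with migration, adjusted for the three-level approach factor, with a 95% confidence interval.
- Keep the by-approach coefficients.
- Keep the raw pooled coefficient, labelled as mixing between-approach and within-approach variation.

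The cost is one SAP sentence, a small addition to the program and two degrees of freedom (half-width 0.209 instead of 0.207 at n = 90). No new data are needed.

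There are two limits to state with the result. A single partial correlation assumes a common relation across approaches, which the by-approach coefficients can check only roughly. Adjusting for approach also does not remove surgeon or site differences within an approach.
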